3.7 Safety Analyses

Adverse events (AEs) will be coded to the corresponding system organ class (SOC) and preferred terms (PT) using current version of the Medical Dictionary for Regulatory Activities (MedDRA). The incidence, severity, and relationship to investigational product will be summarized. Specific AEs will be counted once for each subject for calculating percentages. In addition, if the same AE occurs multiple times within a particular subject, the highest severity and level of relationship observed will be reported. If any associations of interest between AEs and baseline characteristics are observed, additional stratified results may be presented. All treatment-emergent adverse events (TEAEs) will be summarized overall, as well as categorized by MedDRA SOC and PT.

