3.3.3 Investigational Product Exposure

Descriptive statistics of the investigational product exposure will be presented based on the measures outlined in Table 3.3.3-1.

Table 3.3.3-1 Investigational Product Exposure Summary		
Population (Period)		
As-treated population (RCP only)	Open-label population (OLP only)	Any MEDI-551 population (Any MEDI-551 exposure only)

 Extent of exposure (in days) – descriptive statistics Number of doses [1, 2]-n (%) Dose amount (mg) – descriptive statistics Dose amount adjusted for weight (mg/kg) based on most recent weight – descriptive statistics 	
 Extent of exposure (in days) – descriptive statistics Extent of exposure (in days) categories defined by every 26 weeks or 183 day interval – n (%) Number of MEDI-551 doses excluding placebo dose at OLP Day 15 [1, 2, 3, 4, 5 etc. and mean/subject] – n(%) and descriptive statistics Received placebo dose at Day 15 – n (%) 	
 Extent of exposure (in days) – descriptive statistics Extent of exposure (in days) categories defined by every 26 weeks or 183 day interval - n (%) Number of MEDI-551 doses excluding placebo dose at OLP Day 15 [1, 2, 3, 4, 5 etc. and mean/subject] – n(%) and descriptive statistics
Extent of exposure definition		
Last RCP dose date – 1 st RCP dose date + 60 ^a	Last MEDI-551 dose date (OLP) – 1 st OLP dose date + 60 ^a	Last MEDI-551 dose date – 1 st MEDI-551 dose date + 60 ^a
Person-year definition for individual subject ^b		
(Date of last day before OLP or SFP – 1 st RCP dose date + 1)/365.25	(Date of last day before SFP – 1 st OLP dose date + 1)/365.25	(Date of last day before SFP – 1 st MEDI-551 dose date + 1)/365.25
^a based on 5 half-lives		
^b total person-years will be calculated as the sum of the person-years for individual subject		

If entire dose was administered, the dose amount (mg) at a specific visit will be either 0 or 300 mg depending on what treatment the subject had received. If not, the dose will be estimated based on actual volume administered. For example, if a subject receives 175ml (instead of the full 250 mL), the dose amount (mg) will be estimated as $= 300 \times \frac{175}{250} = 210$ provided the subject received MEDI-551.

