3.4 Efficacy Analyses

3.4.1 Primary Efficacy Endpoint Analyses

3.4.1.1 Primary Efficacy Endpoint

The primary endpoint is the time (days) from Day 1 to onset of an AC-determined NMO/NMOSD attack on or before the end of RCP (Day 197/discontinuation visit). The definition of an NMO/NMOSD attack is the presence of a new symptom(s) or worsening of an existing symptom(s) related to NMO/NMOSD that meets at least ONE of the protocol-defined criteria for an NMO/NMOSD attack provided in Table 3.4.1.4-1. This table is displayed only to pre-specify the severity grading attached to each criterion which is not presented in the protocol to eliminate any possible bias by the site when assessing for an attack. Onset day is defined as when the subject visits the site for possible attack assessment (ie, the initiation of attack assessment visit).

Per protocol requirement, sites are required to schedule an Assessment Visit with the subject within 72 hours of symptoms being reported or identified and all assessments are to be completed within 5 days of this visit. However, not all AC-determined attacks may fall within these time windows; hence a broader window will be used for primary analysis. **Only AC-determined attacks with an assessment visit scheduled within 120 hours (5 days) of reporting symptoms AND all necessary assessments done within 10 days of an Assessment Visit will be included in the primary analysis.** Other AC-determined attacks not included in primary analysis will be included in other supportive analyses.

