3.5.4 Other Efficacy Analyses

Table 3.5.4-1 provides an overview of additional efficacy analyses to be performed.

Table 3.5.4-1 Additional Efficacy Analyses

Type of analysis	Analysis Method	Analysis population
Cox proportional hazards model of investigator-determined NMO/NMOSD attack	Similar analysis as primary endpoint but based on investigator-determined NMO/NMOSD attack.	ITT
Time to either AC-determined NMO/NMOSD attacks or rescue therapy	An exploratory analysis of time to adjudicated AC-determined NMO/NMOSD attacks or rescue therapy (where an attack has not been determined by AC) during the RCP will be conducted by considering administration of rescue therapy as an event of interest. Subjects who never experience an NMO/NMOSD attack (determined by AC) nor received any rescue therapy will be censored for this analysis. In the instance where a subject never experiences an AC-determined NMO/NMOSD attack, the time to rescue therapy will be used for this analysis.	ITT
Type of NMO/NMOSD attacks	Number (%) of subjects with different types of NMO/NMOSD attacks (ON, Myelitis, Brain and Brainstem) (subjects will be included in multiple categories if applicable): 
 • Based on AC-determined attacks • Based on investigator-determined attacks 	ITT
Summary of individual criteria of NMO/NMOSD attack	Number (%) of subjects meeting each of the protocol-defined criteria for NMO/NMOSD attack will be summarized descriptively (subjects will be included in multiple categories if applicable): 
 • Based on AC-determined attacks • Based on investigator-determined attacks 	ITT
Criteria based severity of attack	Number (%) of subjects meeting each of the protocol-defined criteria of an AC-determined NMO/NMOSD attack will be summarized broken down by the severity [mild, moderate, severe] defined in Table 3.4.1.4-1	ITT
Attack type based severity	Number (%) of subjects meeting an AC-determined NMO/NMOSD attack will be summarized broken down by the severity [minor, major] defined in Appendix 4	ITT

Table 3.5.4-1 Additional Efficacy Analyses

Type of analysis	Analysis Method	Analysis population
Attack recovery	Number (%) of subjects meeting an AC-determined NMO/NMOSD attack will be summarized broken down by the recovery status [minor, major] defined in Appendix 4	ITT

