3.7.1 Adverse Events

The definitions of TEAE provided in Table 3.7.1-1 will be used for analysis of adverse events based on different study periods. Figure 3.7.1-1 provides a visual representation of TEAEs during different study periods. The AE(RCP), AE(OLP) and AE(SFP) represent TEAEs during RCP, OLP and SFP, respectively.

Table 3.7.1-1 Definition of Treatment-Emergent AEs (TEAEs)

RCP	OLP	SFP	Any MEDI-551 Exposure
For subjects entering the OLP, a TEAE will be defined as any AE with an onset time on or after the first dose of IP in the RCP up to the time prior to the first OLP dose.	A TEAE will be defined as any AE with an onset time on or after 1st dose of OLP up to and including the day prior to the SFP entry.	A TEAE will be defined as any AE with an onset on or after entry to SFP.	A TEAE will be defined as any AE with onset on or after the first MEDI-551 dose (either RCP or OLP) up to and including the day prior to entry to SFP.
For subjects entering the SFP after RCP, a TEAE will be defined as any AE with an onset on or after the first dose of IP in the RCP up to and including the day prior to the entry to SFP.	---		
For subjects not entering the OLP or SFP after RCP, a TEAE will be defined as any AE with an onset on or after the first dose of IP in the RCP			

[figure not shown]

Figure 3.7.1-1 Visual definition of TEAEs during different study periods

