3.7.1.1 Adverse Events of Special Interest

The following Adverse Events of Special Interest (AESI) will be summarized; the infusion related reaction, anaphylactic reaction and hypersensitivity will be collected from the case report form. Infections will be identified by the corresponding System Organ Class (SOC); for remaining AESIs, relevant search criteria will be established prior to database lock.

- Infusion Related Reaction
- Anaphylactic Reaction
- Hypersensitivity
- Infections
- Hepatic Function Abnormality
- Cytopenia
- Opportunistic Infection
- Progressive Multifocal Leukoencephalopathy (PML)

Symptoms corresponding to infusion-related reaction will be summarized separately and will not be combined with TEAE analysis.

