3.7.2 Analysis of Adverse Events and Serious Adverse Events

Treatment-Emergent adverse events and serious adverse events during RCP, OLP, SFP and any MEDI-551 exposure will be summarized as described in Table 3.7.2.2-1.

TEAEs per 100 Person-years for a specific reporting period will be calculated as

$$= 100 \times \frac{\text{Total number of TEAEs for specific reporting period}}{\text{Total Person years for specific reporting period}}$$

See Table 3.3.3-1 for definition of person-years.

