3.7.2.2 Subgroup Analyses of Adverse Events

Treatment-Emergent adverse events (by SOC and PT) during RCP will be summarized by sex (male vs female).

Table 3.7.2.2-1 Type of TEAE Analysis by Period

Type of TEAE Analysis	RCP	OLP	SFP	Any MEDI-551 Exposure
Overall Summary of TEAEs	X	X	X	X
TEAEs by SOC and PT	X	X	X	X
IP Related TEAEs by SOC, PT	X	X		X
TEAEs with severity ≥ Grade 3 by SOC and PT	X	X		X
TESAEs by SOC and PT	X	X	X	X
TEASEs by Seriousness Criteria	X	X	X	X
TEAEs resulting in permanent discontinuation of the IP by SOC and PT	X	X		X
TEAEs resulting in death by SOC and PT	X	X	X	X
TEAEs (≥5% in MEDI-551)	X	X		X
TEAEs by SOC, PT and by Highest Severity	X	X	X	X
IP Related TEAEs by SOC, PT and by Highest Severity	X	X		X
IP Related TEAEs with Severity ≥ Grade 3 by SOC and PT	X	X		X
IP Related TESAEs by SOC and PT	X	X		X
TEAEs with Severity ≥ Grade 3 and/or TESAEs by SOC and PT	X	X		X
IP Related TEAEs with Severity ≥ Grade 3 and/or TESAEs by SOC and PT	X	X		X
TEAEs by PT sorted by frequency in MEDI-551 group	X	X		X
TEASEs by Preferred Term Sorted by Frequency	X	X	X	X
All deaths	X	X	X	X
AESI by SOC and PT	X	X	X	X
TEAEs per 100 Person-years	X	X		X
TESAEs per 100 Person-years	X	X		X
‘X’ represents that an analysis will be performed for this period				

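### Infections in the randomised period are planned as percentages of subjects, although an effective drug would leave placebo subjects with shorter follow-up; add an infection rate censored at attack or rescue

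*SAP*

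**What the plan says.** - **Counting rule.** SAP 3.7: "Specific AEs will be counted once for each subject for calculating percentages".
- **Infections.** SAP 3.7.1.1 lists infections (identified by organ class) and opportunistic infection as adverse events of special interest (AESIs) and says they will be summarised, without naming a method. Their only row in Table 3.7.2.2-1 is "AESI by SOC and PT".
- **Person-year rates.** The same table marks TEAEs and TESAEs per 100 person-years for the RCP. The numerator in SAP 3.7.2 is "Total number of TEAEs for specific reporting period". Neither row carries the organ-class and preferred-term label used elsewhere in the table. RCP person-years run from first dose to "Date of last day before OLP or SFP" (Table 3.3.3-1).
- **Event window.** For subjects who enter the open-label period (OLP), RCP events are those with onset "on or after the first dose of IP in the RCP up to the time prior to the first OLP dose" (Table 3.7.1-1). Otherwise the window closes the day before safety follow-up starts.
- **End of the RCP.** Under Protocol 6.3, a subject with an adjudicated attack has completed the RCP. Adjudication takes 14 (+3) days from the Assessment Visit (Protocol 3.1.1.3), and OLP entry should follow within 28 days of confirmation (Protocol 4.2.2.2).

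**The concern.** MEDI-551 depletes B cells, so infection is a central safety question. Every OLP subject receives the drug, which leaves the RCP as the only infection comparison against placebo. The efficacy endpoint itself ends RCP follow-up. If the drug prevents attacks, placebo subjects leave sooner and have less time in which an infection can be counted. A percentage of subjects does not correct for this, and a rate pooled over all TEAEs cannot show whether infections differ.

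With no drug effect on infection, the percentage table would then tend to show somewhat more infections on MEDI-551. A second force acts the other way. Rescue therapy (IV corticosteroids, IVIG, plasma exchange) would be more frequent on placebo and may change infection risk between the attack and OLP entry.

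**Working it through.** **Inputs from the plan (SAP Appendix 1).** Placebo attack hazards are 1.5 per year (seropositive) and 1.0 (seronegative). HR 0.4 gives 0.6 and 0.4 on MEDI-551. The serostatus mix is 80:20, allocation is 3:1, and F = 197/365 = 0.54 year.

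**Check of the plan's own figure.** (1.960 + 1.282)² / (ln 0.4)² × 16/3 = 66.7, rounded up to 67 events. This reproduces.

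**Assumed inputs.** The lag x from attack to OLP entry is 17 days (adjudication only) or 45 days (17 + 28). The infection hazard h is the same in both arms, at 0.2 to 1.0 per year. Hazards are constant, and there is no other dropout.

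**Mean RCP time.** For attack hazard λ, let p = 1 − exp(−λF). Mean days = 365p/λ + x·p.

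- Placebo: p = 0.555 and 0.417, giving 135.0 and 152.2 days without lag, or 138.5 weighted. Weighted p is 0.527. Adding 17 × 0.527 gives 147.4 days; adding 45 × 0.527 gives 162.2.
- MEDI-551: p = 0.277 and 0.194, giving 168.3 and 177.2 days, or 170.1 weighted. Weighted p is 0.260. Adding the lags gives 174.5 and 181.8 days.

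**Crude percentage.** P(no infection) = exp(−(λ+h)F) + [λ/(λ+h)]·[1 − exp(−(λ+h)F)]·exp(−h·x/365).

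Example for placebo, h = 0.5, lag 17, where exp(−0.5 × 17/365) = 0.977:

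- Seropositive: 0.340 + 0.75 × 0.660 × 0.977 = 0.824, so 17.6% have an infection.
- Seronegative: 0.445 + 0.667 × 0.555 × 0.977 = 0.807, so 19.3%.
- Weighted 80:20: 18.0%.

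| Lag | Placebo, h = 0.5 | MEDI-551, h = 0.5 | Ratio | Ratio over h = 0.2 to 1.0 |
|---|---|---|---|---|
| 17 days | 18.0% | 21.1% | 1.17 | 1.16 to 1.18 |
| 45 days | 19.7% | 21.9% | 1.11 | 1.10 to 1.12 |

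**Against sampling error.** With 63 vs 189 subjects (252 split 1:3), the standard error of the difference is √(0.180 × 0.820/63 + 0.211 × 0.789/189) = 5.7 points at lag 17, and 5.8 points at lag 45. The gaps of 3.1 and 2.2 points are 0.54 and 0.38 of a standard error.

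**Infection hazard multiplied by m after an attack** (h = 0.5; true drug effect on infection is nil, so the right answer is 1.00):

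| m | Lag | Crude ratio | Rate to end of RCP window | Rate censored at attack or rescue |
|---|---|---|---|---|
| 1 | 17 / 45 | 1.17 / 1.11 | 1.00 / 1.00 | 1.00 |
| 2 | 17 / 45 | 1.134 / 1.039 | 0.967 / 0.931 | 1.00 |
| 4 | 17 / 45 | 1.072 / 0.941 | 0.913 / 0.840 | 1.00 |

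**Other sensitivities (m = 1).**

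- Attack HR 0.6: crude ratio 1.07 to 1.11.
- Attack HR 1: 1.00.
- 20% of subjects have the RCP closed early (assumed): 1.16 (lag 17) or 1.10 (lag 45).
- Attack-prone subjects are also infection-prone (shared gamma frailty, variance 0.5, assumed): crude 1.21 or 1.13, censored rate 1.07.

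**The case against.** **Exposure adjustment is already planned.** A reader might infer that RCP adverse events receive none. The documents do not support that: total TEAEs and TESAEs have person-year rates in the RCP, and the rows do not exclude a breakdown by organ class. This stands, and it narrows the gap to a missing infection-level analysis. It does not close it, because nothing commits the sponsor to that breakdown.

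**Other AESIs.** A reader might extend the point to every AESI that accrues over time. For cytopenia and hepatic abnormality that goes too far: SAP 3.7.3 plans laboratory toxicity by visit, which compares the arms at the same study time. Infusion reactions follow the doses on Days 1 and 15, so unequal RCP length matters little for them.

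**The obvious remedy can be worse.** In three of the four scenarios above with m above 1, a simple rate to the end of the RCP window is further from 1.00 than the crude percentage (for example 0.931 against 1.039), and it errs in the drug's favour. This stands, so that rate should not be the main addition. The censored rate is 1.00 throughout that table, though not under shared frailty. There, with m = 2 and lag 45, it is 1.07 against a crude 1.05.

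**Inputs.** The documents give no infection hazard, and the attack hazards come from the 212-subject calculation. The masked data imply roughly 67/227 = 29.5% with attacks. Rescaling to that at HR 0.4 lowers the crude ratio at h = 0.5 only slightly, to 1.15 (lag 17) or 1.10 (lag 45).

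**Conclusion.** The point holds for infections and opportunistic infections in the RCP. Their planned summary does not allow for unequal follow-up, and an effective drug makes follow-up unequal. With equal infection hazards and no change in hazard after an attack, the crude ratio would be about 1.10 to 1.18. If rescue raises infection risk, the ratio shrinks and can fall below 1 (0.94 with a fourfold rise and a 45-day lag).

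These figures rest on the plan's attack hazards, an assumed infection hazard and an assumed lag. The effect disappears if the drug does not reduce attacks. It is well inside sampling error, and the tables are descriptive.

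A reader might infer that the plan conceals harm or weakens the trial's conclusions. Neither follows: in the simplest case the percentages overstate infections on MEDI-551, and the efficacy analyses are untouched. This is worth considering as a cheap improvement.

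**What to change.** Keep all existing tables. In SAP 3.7.2 and Table 3.7.2.2-1, add for the RCP, by arm:

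- **Main addition.** Subjects with a first infection (and first opportunistic infection, where counts allow) per 100 person-years at risk, or 1 minus Kaplan-Meier. Censor at the earlier of attack onset or first rescue therapy, and otherwise at the end of the RCP event window. State the assumptions: infection risk independent of attack and RCP exit, and a roughly constant hazard if a rate is used.
- **Optional support.** The same rate to the end of the RCP event window, labelled as including time after rescue and liable to favour MEDI-551 if rescue raises infection risk.

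New rate rows for cytopenia and hepatic abnormality are not needed. PML cases can be listed, and infusion reactions can stay as percentages.

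No new data are required. Event dates (Protocol Appendix 12) and rescue dates (Protocol 4.7.1) are collected. Attack onset is defined in SAP 3.4.1.1: "Onset day is defined as when the subject visits the site for possible attack assessment". Table 3.5.4-1 already plans "Time to either AC-determined NMO/NMOSD attacks or rescue therapy".

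The cost is one or two descriptive tables and slightly fewer events. At 0.5 per year with no post-attack change, about 10.6 first infections are expected on placebo with censoring (63 × 16.9%, the no-lag percentage), against 11.3 to 12.4 in the full window (63 × 18.0% and 63 × 19.7%).

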3.7.1 Adverse Events

The definitions of TEAE provided in Table 3.7.1-1 will be used for analysis of adverse events based on different study periods. Figure 3.7.1-1 provides a visual representation of TEAEs during different study periods. The AE(RCP), AE(OLP) and AE(SFP) represent TEAEs during RCP, OLP and SFP, respectively.

Table 3.7.1-1 Definition of Treatment-Emergent AEs (TEAEs)

RCP	OLP	SFP	Any MEDI-551 Exposure
For subjects entering the OLP, a TEAE will be defined as any AE with an onset time on or after the first dose of IP in the RCP up to the time prior to the first OLP dose.	A TEAE will be defined as any AE with an onset time on or after 1st dose of OLP up to and including the day prior to the SFP entry.	A TEAE will be defined as any AE with an onset on or after entry to SFP.	A TEAE will be defined as any AE with onset on or after the first MEDI-551 dose (either RCP or OLP) up to and including the day prior to entry to SFP.
For subjects entering the SFP after RCP, a TEAE will be defined as any AE with an onset on or after the first dose of IP in the RCP up to and including the day prior to the entry to SFP.	---		
For subjects not entering the OLP or SFP after RCP, a TEAE will be defined as any AE with an onset on or after the first dose of IP in the RCP			

[figure not shown]

Figure 3.7.1-1 Visual definition of TEAEs during different study periods

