3.2.2 Dose Rationale

The 300 mg dose of MEDI-551 was selected to achieve complete peripheral B-cell depletion. Based on existing PK and B-cell PD data from Study MI-CP200, a fixed dose of 300 mg MEDI-551 given on Day 1 and Day 15 is predicted to fully deplete peripheral blood B cells to undetectable levels and maintain B-cell suppression for 28 weeks, therefore sustaining B-cell depletion for the duration of the RCP. In theory, an initial dose of MEDI-551 will deplete the peripheral blood B cells; however, additional B cells will then recirculate out of the lymphoid tissues. The second dose of MEDI-551 on Day 15 is timed to deplete the newly recirculated B cells from the peripheral blood.

This dose regimen is supported by clinical data from other B-cell depleting mAbs, where IV dosing on Day 1 and Day 15 will provide optimal B-cell depletion in both blood and tissues ([Huffstutter et al, 2011](#); [Hauser et al, 2008](#); [Bar-Or et al, 2008](#); [Kappos et al, 2011](#)).

A fixed dose of 300 mg MEDI-551 administered on OLP Day 1 (and OLP Day 15 for subjects who received placebo in the RCP) and then every 26 weeks is predicted to fully deplete peripheral blood B cells to undetectable levels and maintain B-cell suppression for the dose interval of the OLP (Figure 2).

Figure 2 PD Model Simulation Supporting Dosing Regimen

PD = pharmacodynamic; Q26W = every 26 weeks

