4.2.6 Safety Follow-up Period

Table 10 shows all procedures to be conducted during the SFP.

The SFP will start when a subject prematurely discontinues from the RCP or the OLP. The length of the SFP will be determined by the time elapsed from the time of the last dose of the investigational product to the time of the premature discontinuation, to complete a total of 52 weeks. Subjects who prematurely discontinue during the RCP will continue with the study assessments until Day 197, unless the consent was specifically withdrawn for further study assessments.

Table 10 Schedule of Procedures for Safety Follow-up Period

Study Period	Follow-up Period
Visit Number	Every 3 months for a total of 1 year after last dose of investigational product (± 14d)
Procedure/Study	
Vital signs	X
C-SSRS (“Since Last Visit” version)	X
Whole blood for flow cytometry (B-cell count and cell subsets)	X
Total Ig, IgM, IgG, IgA, and IgE	X
MEDI-551 ADA	X
Assessment of AEs/SAEs	X

ADA = anti-drug antibody; AE = adverse event; C-SSRS = Columbia Suicide Severity Rating Scale; d = day(s); Ig A/E/G/M = immunoglobulin A/E/G/M; SAE = serious adverse event

[figure not shown]

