3.2 Analysis Populations

The analysis populations are defined in Table 3.2-1. The number of subjects (without percentage) by stratification group and treatment group will be tabulated for each of these analysis populations.

Table 3.2-1 Analysis Populations	
Population	Description
Intent-to-treat (ITT) population	Subjects who are randomized and receive any IP will be included in the ITT population to be analyzed according to their randomized treatment group regardless of whether subjects receive an IP different from that they were randomized to.
As-treated population	Subjects who receive any IP will be included in the as-treated population, analyzed according to treatment received. Specifically, subjects randomized to MEDI-551 who received all placebo doses will be included in the placebo group; conversely, subjects randomized to placebo who received at least one dose of MEDI-551 will be included in the active treatment group.
Open-label population	Subjects who receive at least one dose of MEDI-551 during the OLP will constitute this population.
Any MEDI-551 population	Subjects who receive at least one dose of MEDI-551 (either in the RCP or OLP).
Non-OLP population	Subset of as-treated population who do not roll over to OLP

Table 3.2-2 provides an overview of different type of analyses (demographics, safety and efficacy) by analysis populations and study periods.

Table 3.2-2 Overview of Analysis Domains by Analysis Populations and Study Periods

Period	Population				Any MEDI-551
	ITT	As-Treated	Non-OLP	Open-label	
RCP	
 Demographics/ Baseline characteristics Subject disposition Medical and disease history Physical/Neurological Examination Prior and concomitant medication, steroid tapering Efficacy, Rankin scale HCRU, SF-36, Pain 	
 Exposure to investigational product Adverse events C-SSRS Safety Lab/Flow cytometry lab/IgG Immunogenicity Vital sign, weight, ECG 	---	
 Demographics/Baseline characteristics Medical and disease history Physical/Neurological Examination Prior Medication 
The information is based on baseline of RCP but will be presented only for Open-label population
	
SFP	---		
 Subject disposition Concomitant medication Adverse events C-SSRS Flow cytometry lab/IgG Immunogenicity Vital signs 		

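### No cumulative MEDI-551 safety table runs from first dose to end of study, and the SAP does not settle whether safety follow-up events after OLP exit are tabulated

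*SAP*

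**What the plan says.** **Event windows (SAP 3.7.1, Table 3.7.1-1).** Any MEDI-551 exposure: onset "on or after the first MEDI-551 dose (either RCP or OLP) up to and including the day prior to entry to SFP". OLP: "any AE with an onset time on or after 1st dose of OLP up to and including the day prior to the SFP entry". SFP: "A TEAE will be defined as any AE with an onset on or after entry to SFP", with no population named.

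**Person-years (SAP 3.3.3, Table 3.3.3-1).** For the OLP and for any MEDI-551 exposure, the end point is "Date of last day before SFP". There is no SFP person-year definition.

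**Populations (SAP 3.2).** Table 3.2-2 "provides an overview of different type of analyses (demographics, safety and efficacy) by analysis populations and study periods". In the extracted text its SFP row lists adverse events, C-SSRS, flow cytometry and IgG, immunogenicity and vital signs under the Non-OLP population. Table 3.2-1 defines that population as "Subset of as-treated population who do not roll over to OLP".

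**Planned tables (SAP 3.7.2 and Table 3.7.2.2-1).** The SFP is one of four reporting periods. Its column is marked for the overall summary, TEAEs and TESAEs by SOC and PT, seriousness criteria, highest severity, fatal TEAEs, all deaths and AESIs. It is blank for every IP-related table and for both tables of rates per 100 person-years.

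**Protocol.** Section 4.8.4.1 carries the TEAE summary from the first infusion to the end of the study. Section 6.3 places that end at the last subject's completion of the 52-week SFP. Section 5.4.1 collects adverse events through the SFP, and Table 10 schedules visits "Every 3 months for a total of 1 year after last dose of investigational product".

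**The concern.** The drug's effect is meant to outlast the dose. Protocol 3.2.2 predicts that B-cell suppression in the OLP lasts the whole 26-week dose interval. A subject who leaves the OLP soon after a dose therefore spends most of the predicted suppression period in the SFP. The SAP's AESI list in 3.7.1.1 includes infections, opportunistic infections, cytopenia and PML, for which late onset is a natural question.

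The table that looks like the whole-programme safety summary, Any MEDI-551, closes before that time begins. If the SFP tables are also limited to subjects who never entered the OLP, the repeatedly dosed subjects have no tabulated post-treatment safety, and the SFP B-cell and immunoglobulin summaries omit them too. What is at stake is the completeness of cumulative counts of serious events, deaths and AESIs in the final analysis.

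**Working it through.** The plan states no figure on this point, so there is none to reproduce. The check is a cross-reading, followed by arithmetic for size.

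**Step 1: trace one event.** A subject takes an OLP dose, leaves the OLP, enters the SFP, and has a serious infection four weeks later.

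| Reporting period | Does the window admit the event by date? |
|---|---|
| RCP | No, it closed before the first OLP dose |
| OLP | No, it closed the day before SFP entry |
| Any MEDI-551 | No, it closed the day before SFP entry |
| SFP | Yes |

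Only the SFP tables can hold the event. If they cover every SFP entrant, it appears among TEAEs, TESAEs and AESIs. If they cover only the Non-OLP population, it does not, and it is left to the listings that SAP 3.1 promises for all data. On either reading it is absent from the Any MEDI-551 tables.

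**Step 2: which population?** SAP 3.7.1, 3.7.2 and Table 3.7.2.2-1 name none for the SFP. Table 3.2-2, as extracted, names Non-OLP. Column order supports this, since the OLP row's items fall one column later, under Open-label. But the table is broken across pages, the Open-label cell in the SFP row is blank rather than dashed, and Figure 3.7.1-1 is not shown. A merged Non-OLP/Open-label cell cannot be ruled out.

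**Step 3: follow-up outside the cumulative window.** Inputs: 52 weeks of follow-up after the last dose (Protocol 4.2.6), a 26-week OLP dose interval (Protocol 3.2.2) and at most 252 subjects (Protocol 4.1.1). If a subject leaves the OLP *w* weeks after the last dose, with *w* from 0 to 26:

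- SFP follow-up = 52 − *w* weeks.
- Part inside the predicted suppression interval = 26 − *w* weeks.
- Person-years if all 252 roll over and complete the SFP = 252 × (52 − *w*)/52.

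| *w* (weeks) | SFP weeks | Of which in predicted suppression | Person-years, upper bound |
|---|---|---|---|
| 0 | 52 | 26 | 252 × 52/52 = 252 |
| 13 | 39 | 13 | 252 × 39/52 = 189 |
| 26 | 26 | 0 | 252 × 26/52 = 126 |

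**Step 4: how many subjects?** The documents give no roll-over proportion, so *r* is an assumption, taken as equal in both arms. With 3:1 allocation of 252 (189 MEDI-551, 63 placebo), the Any MEDI-551 population is 189 + 63*r* and the OLP population is 252*r*. The OLP share is 252*r*/(189 + 63*r*).

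| *r* | OLP | Any MEDI-551 | OLP share |
|---|---|---|---|
| 30% | 75.6 | 207.9 | 36% |
| 50% | 126.0 | 220.5 | 57% |
| 70% | 176.4 | 233.1 | 76% |
| 90% | 226.8 | 245.7 | 92% |
| 100% | 252.0 | 252.0 | 100% |

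The share passes one half when 252*r* > 0.5 × (189 + 63*r*), that is, *r* > 94.5/220.5 = 42.9%. At *r* = 90%, the Non-OLP population would be about 25 of 252.

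**The case against.** The strongest reply is that the SAP does plan SFP incidence tables, including serious events, deaths and AESIs, and that nothing in SAP 3.7 restricts them. The OLP definition itself anticipates entry to the SFP from the OLP. A reader might infer from Table 3.2-2 that SFP events in rolled-over subjects reach no incidence table. The documents do not support a statement that firm, because it rests on a damaged table whose cell may be merged. This part of the reply stands.

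A second reply is that the present window gives a coherent on-treatment rate. Events and person-years stop on the same day, and standard NMO treatment is allowed in the SFP, so keeping that period apart is defensible. This also stands. A reader might infer that the rates are understated, or that the cut is informative because adverse events drive SFP entry. Extending the window adds both events and time, and nothing shows that the rate would rise. Subjects also enter the SFP by choice or when the sponsor ends the OLP.

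A third reply is that separate period tables could together satisfy Protocol 4.8.4.1. That holds only if the SFP tables include subjects leaving the OLP, which is the unsettled point. Even then, no table counts each MEDI-551 subject once from first dose to end of study, and none gives IP-related events or rates for the SFP.

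**Conclusion.** The point holds in two parts.

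1. On unbroken text, the Any MEDI-551 events and person-years both end before the SFP. No cumulative MEDI-551 safety table therefore reaches the end of study, although the protocol carries TEAE summaries that far and the data are collected.
2. On the text as extracted, the SAP is at minimum unreconciled on whether SFP events after OLP exit are tabulated.

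The size is 26 to 52 weeks of follow-up per subject leaving the OLP, of which 0 to 26 weeks lie inside the predicted suppression interval. The total of 126 to 252 person-years is a ceiling that assumes 252 subjects, full roll-over and completed follow-up. Since enrollment was stopped on the DMC's recommendation (Protocol section 9, Amendment 6), the true figure may be well below it.

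Two further inferences should not be drawn. A reader might conclude that most treated subjects are affected. That is plausible, because RCP completers, subjects with an AC-determined attack and subjects in the RCP at an early stop are all offered the OLP, but it needs roll-over above about 43%, which the documents do not give. A reader might also apply the protocol's prediction that dosing will "maintain B-cell suppression for 28 weeks" to subjects leaving the OLP. That prediction belongs to the two-dose RCP course; for the OLP the protocol predicts suppression over the dose interval.

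**What to change.** **(a) Settle the SFP population.** State in SAP Tables 3.2-1 and 3.2-2 that SFP analyses include every subject who enters the SFP, whether from the RCP or the OLP, grouped as any MEDI-551 versus placebo only.

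**(b) Add a through-end-of-study window.** Define an Any MEDI-551 TEAE and person-year window from the first MEDI-551 dose to the last SFP contact. Use it for SAEs, deaths and the AESIs of infection, opportunistic infection, cytopenia and PML. Keep the present window, labelled as the on-treatment version, and show the two side by side.

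**(c) Handle new treatment.** Late events may be confounded by NMO treatment started in the SFP. Where medication dates exist, add a version truncated at the start of new immunosuppressant treatment. Availability needs checking: Protocol 4.7 records medication to the final visit and SAP 3.3.4.1 defines SFP concomitant medication, but Protocol Table 10 does not list its collection.

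The cost is SAP wording and some additional tables. The adverse event data are already collected, and no visit or procedure changes.
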